5.2.1 Brachial Artery Flow Mediated Dilation (FMD) Without Nitroglycerin

The methods of assessment of endothelial function via FMD will be performed following guidelines. Vascular reactivity will be measured noninvasively using vascular ultrasound imaging. Flow and diameter changes of the brachial artery will be assessed by Duplex ultrasound using a high-resolution linear array transducer. The difference between the maximum brachial artery diameter (BAD) post-occlusion and the baseline diameter is expressed as a percentage (%BAD). Generally, %BAD values below 5-7% represent endothelial dysfunction, which is associated with CV risk factors, future CVD and mortality. Effective treatment of risk factors may improve endothelial function. Given its reversibility and non-invasiveness, brachial artery FMD is attractive as an assessment tool to monitor strategies to reduce CVD.

5.2.2 Peripheral Arterial Tone (PAT)

PAT measured by the EndoPAT 2000 device is a non-invasive method to assess endothelial function. It is a standardized, rapid, and easy to apply method, and has been found to correlate with multiple traditional CV risk factors and to be responsive to interventions. PAT is a validated alternative measure to brachial arterial FMD in assessing endothelial function, and is less operator-dependent than FMD. FMD directly measures the dilation capability of the large-conduit artery, whereas PAT measures flow response hyperemia, which is related to endothelial function of small arteries of microcirculation. PAT measures endothelium-mediated changes in vascular tone using bio-sensors placed on fingertips. Changes in arterial tone are elicited by creating a down-stream hyperemic response of the brachial artery from arm occlusion. Contra-lateral arm measurements are used to control for concurrent non-endothelial dependent changes in vascular tone. The semi-automatically calculated result is an index of endothelial function.

5.2.3 Safety Profile: Adverse Event Outcomes:

All adverse event (AE) and serious adverse event (SAE) data will be collected by separate study personnel from those collecting other outcomes; we will document AE and SAE diagnosis, date of onset and resolution, severity, whether it was unexpected or related to intervention; whether the blind was broken; and outcome. Specific AE data will include all common side effects of sildenafil as per Micromedex.

5.3 Secondary endpoint

- Specific Aim 2: To determine whether sildenafil use in RA patients is associated with improvement in serum atherosclerosis biomarkers.

Biomarkers for endothelial dysfunction, atherosclerosis and inflammation will be measured as follows:

High-sensitivity CRP (hsCRP), ESR, rheumatoid factor (RF), and anti-cyclic citrullinated peptide antibody (CCP) will be measured in all patients, using standard clinical laboratory protocols. Blood nitrite levels will be measured using chemiluminescence. The following additional selected biomarkers

involved in endothelial dysfunction and atherosclerosis will be measured in all subjects using enzyme linked immunosorbent assay (ELISA): leukocyte adhesion molecules (E-selectin, ICAM-1, VCAM-1), CD40 ligand (CD40L), interleukin-6 (IL-6), matrix metalloproteinase-9 (MMP-9), and myeloperoxidase (MPO).

7. STUDY DESIGN

7.1 Overview

After obtaining written informed consent, eligible participants will be randomized in a 1:1 fashion to receive either sildenafil 50 mg orally once daily or placebo orally once daily for 3 months. After 3 months, all subjects will undergo a 2-week washout period. Then, subjects in each group will cross over to the respective group (i.e., those receiving sildenafil will receive placebo, and vice versa), for an additional 3 months. This cross-over design will aid in recruitment feasibility and was based in part on known patient preferences from other trials, since all subjects will receive a potentially beneficial drug at some point during the study. It also allows for up to 80 recruited subjects to contribute safety data for Specific Aim 1. Since sildenafil has a half-life of only 4 hours and pharmacodynamics effects of only 8 hours, and there will be a 2-week washout period, there is unlikely to be a substantial carry-over effect of the drug during the cross-over phase. Any potential for carry-over effect will also be accounted for by including treatment order in our statistical models. We will use Stata statistical software to randomly assign treatment status using randomized blocks of size 6.

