Methodology	
This study is designed to investigate the efficacy and safety of sildenafil 50 mg once daily in RA patients with no known history of CVD, but at least one traditional CV risk factor. Patients will be randomized 1:1 to receive either sildenafil or placebo for 3 months, then after a 2-week washout, crossed over to each respective group for an additional 3 months. Vascular studies validated in assessing endothelial dysfunction (brachial artery flow-mediated dilation [FMD]²⁻⁴ and peripheral arterial tone [PAT])⁵ and laboratory studies for selected atherosclerosis biomarkers will be performed at baseline, 3 months pre- and post-washout, and 6 months. Adverse events will be collected to assess sildenafil's safety.

Type of control	Placebo
Number of subjects	Up to 80 randomized subjects (to achieve final total of 60 subjects after expected ~20% drop-out)
Primary variable	Vascular function, determined through brachial arterial flow-mediated dilation (FMD) and peripheral arterial tone (PAT)
Plan for statistical analysis	
For the primary variable, treatment group (sildenafil vs. placebo) is the exposure of interest, with vascular function measures: (1) percent increase in mean maximum brachial artery diameter (%BAD) using FMD (continuous), and (2) mean PAT ratio (continuous) using EndoPAT 2000, as the primary outcomes of interest (measured at 0, 3 months pre- and post-washout, and 6 months). Given the cross-over design, analyses will focus on within-subject comparisons of sildenafil versus placebo periods. All tests will be 2-sided with $\alpha=0.05$. The analysis will use linear mixed models⁶, with a term for treatment order (i.e. randomized initially to sildenafil or placebo), to assess whether %BAD and mean PAT ratio differ significantly between the sildenafil and placebo periods within subjects, adjusting for treatment order and CVD risk factors, baseline RA and CV medication use, disease activity (CDAI) and duration, and baseline levels of %BAD and PAT. Secondary outcomes of interest for Specific Aim 1 are the frequencies of AEs and SAEs. Since the absolute numbers of these events is anticipated to be small, Fisher's exact tests will be used to compare these frequencies between the initial sildenafil and placebo groups.

List of abbreviations

ACE	angiotensin-converting enzyme
ACR	American College of Rheumatology
AE	adverse event
AIDS	acquired immunodeficiency syndrome

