15.1 Statistical Methods for Specific Aims

For **Specific Aim 1**, treatment group (sildenafil vs. placebo) is the *exposure* of interest, with vascular function measures: (1) percent increase in mean maximum brachial artery diameter (%BAD) using FMD (continuous), and (2) mean PAT ratio (continuous) using EndoPAT 2000, as the *primary outcomes* of interest (measured at 0, 3 months pre- and post-washout, and 6 months). Given the cross-over design, analyses will focus on within-subject comparisons of sildenafil versus placebo periods. All tests will be 2-sided with $\alpha=0.05$.

The analysis will use linear mixed models, with a term for treatment order (i.e. randomized initially to sildenafil or placebo), to assess whether %BAD and mean PAT ratio differ significantly between the sildenafil and placebo periods within subjects, adjusting for treatment order and CVD risk factors, baseline RA and CV medication use, disease activity (CDAI) and duration, and baseline levels of %BAD and PAT. Model fit, appropriate assumptions (e.g. normality, linearity, homoscedasticity), and potential collinearity, will be assessed with standard diagnostic plots and variance inflation factors (VIF). If needed, we will explore corresponding transformations of the covariates, and/or (in the case of collinearity) dropping variables from the model. We will address any non-compliance using an intention-to-treat strategy and will conduct a sensitivity analysis to conservatively assess observing how the worst outcome would affect results. We do not anticipate many will have RA medication changes but those participants will be included in the analysis; a secondary sensitivity analysis will add a covariate (at the corresponding time point(s)) to denote (yes or no) whether medication changed during the course of the study. Although we recognize that different types of medication changes may have

different effects on the outcome, we will not have sufficient power to estimate heterogeneity of effects across different types of medication changes.

Secondary outcomes of interest for Specific Aim 1 are the frequencies of AEs and SAE. Since the absolute numbers of these events is anticipated to be small, Fisher's exact tests will be used to compare these frequencies between the initial sildenafil and placebo groups.

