For **Specific Aim 2**, treatment group is again the *exposure* of interest, with multiple continuous biomarkers of atherosclerosis as the *outcomes* of interest. Using the same analysis strategy as Specific Aim 1, linear mixed models will be used for each of these atherosclerosis biomarkers as functions of treatment group status, treatment order, clinically important covariates, and any significant baseline factors. Model fit and assumptions will again be checked via standard diagnostic plots and VIF.

To inform future trials, we will summarize differences in outcome measures from the beginning to end of the washout period, and compared to baseline, with mean (standard deviation) and median (range). P-values will be calculated with paired t-tests or Wilcoxon signed-rank tests for non-normal distributions.

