15.2 Sample Size Justification

We aim to recruit up to 80 subjects to achieve a final sample size of 60 evaluable subjects. For Aim 1, the **sample size of 60** (30 in initial sildenafil group and 30 in initial placebo group), gives 80% power for a relatively small effect size of 0.37 for the change in %BAD in the sildenafil versus placebo periods (using a paired t-test, although we will use a linear mixed model for the analysis). Based on previous studies in diabetes, with equivalent CV risk, the estimated standard deviation (SD) of %BAD is approximately 4. The effect size of 0.37 thus corresponds to a % increase of 1.5%, which is clinically meaningful. We will analyze drop-ins, drop-outs, withdrawals, and non-adherences according to intention-to-treat principles.

For Aim 2, given that we are using the same analysis strategy as Aim 1, the sample size of 60 (30 in each group) again yields 80% power to detect an effect size of 0.37 for the change in a given biomarker. The estimated power (in either aim) corresponding to the final mixed model is difficult to estimate more

specifically since it is unclear how much residual variability will remain after adjusting for other covariates, and/or whether a stronger association will be evident after model adjustment.

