15.4 Interim Analyses

Potential non-compliance (assessed via pill counts) will be analyzed using intention-to-treat strategy, and for missing data, we will conduct a sensitivity analysis to conservatively assess observing how the worst outcome (of %BAD) would affect results. The test of a treatment \times period interaction is not possible in the given cross-over design since it is confounded by the group effect.

We do not anticipate many subjects with RA or CV medication changes, since inclusion criteria state no expected therapy changes over next 6 months. Moreover, such changes are unlikely to occur systematically more often in the initial sildenafil vs. placebo groups. However, in the event there are many with such changes, we will also conduct a secondary sensitivity analysis including them to assure this does not affect results. The %BAD was chosen as the primary outcome on which to calculate sample sizes based on clinical considerations. Specifically, %BAD has been validated longer and in more populations than PAT.

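### Section 7.1 relies on the treatment-order term to handle carry-over, which it cannot do, and the listed Aim 1 and Aim 2 model terms include no period effect (minor)

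*Combined protocol and SAP*

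**What the plan says.** - **Carry-over.** Section 7.1 first gives a pharmacological argument: a 4-hour half-life, effects lasting 8 hours and a 2-week washout. It then adds a statistical one: "Any potential for carry-over effect will also be accounted for by including treatment order in our statistical models".
- **Meaning of treatment order.** Section 15.1 defines it: "The analysis will use linear mixed models, with a term for treatment order (i.e. randomized initially to sildenafil or placebo". The synopsis uses the same definition. It is the randomized sequence.
- **Aim 1 model.** The synopsis describes "adjusting for treatment order and CVD risk factors, baseline RA and CV medication use, disease activity (CDAI) and duration", followed by baseline %BAD and PAT. Section 15.1 gives the same list.
- **Aim 2 model.** Section 15.1 models each biomarker "as functions of treatment group status, treatment order, clinically important covariates, and any significant baseline factors". Neither list names a period or visit effect.
- **Aliasing.** Section 15.4 says that a test of the treatment-by-period "interaction is not possible in the given cross-over design since it is confounded by the group effect".
- **Contrast.** Section 15.1 takes the outcomes at all four visits from baseline to month 6. Section 15.2 powers the study "for the change in %BAD in the sildenafil versus placebo periods". The text does not say whether this means end-of-period values or change within each period.

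**The concern.** In a two-period cross-over the treatment effect comes from within-subject differences. Sequence does not vary within a subject, so it cannot adjust those differences for drug effect left over from period 1. A reader of 7.1 would believe that the model offers a second line of defence behind the washout, and it does not.

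Period is the nuisance term that does act within subjects. A shift common to everyone between the first and second treatment period (season, habituation to the test, equipment drift) enters each subject's sildenafil-minus-placebo difference with opposite signs in the two sequences. If it is not modelled, it adds to the residual variance. It also biases the estimate when the sequences have unequal numbers of completers. Such imbalance can arise here, because section 8.5 does not replace withdrawals. What is at stake is some power and a little accuracy in the primary model, and an incorrect sentence in the design section.

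**Working it through.** **Inputs from the documents.** N = 60 evaluable, 30 per sequence; effect size 0.37; SD 4; 80% power by paired t-test (15.2). Two-sided alpha 0.05 (15.1). Up to 80 randomized (synopsis, 15.2). No replacement (8.5).

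**Assumed, because the documents give no value.** Period shift p = 0.5, 1 or 2 %BAD points; 2 exceeds the 1.5-point target and is an upper extreme. Carry-over L = 0.74 points as an illustration. Completers are a random 60 of 80 (40 per sequence), with dropout unrelated to sequence. The SD of 4 is taken as the SD of the paired difference, as 15.2 uses it: 0.37 x 4 = 1.48, rounded there to 1.5.

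**1. The plan's own figure.** Paired t-test, 59 df, noncentrality 0.37 x sqrt(60) = 2.866: power 80.5%. The stated 80% is reproduced.

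**2. What the sequence term does.** Let D be the true effect and n_S and n_P the completers starting on sildenafil and placebo. The sildenafil-minus-placebo difference has expectation:
- sildenafil first: D - p - L
- placebo first: D + p

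Without a period term the estimate is the mean over all subjects, with expectation D - L x n_S/N - p x (n_S - n_P)/N. Sequence does not appear in it. In a random-intercept model fitted to one simulated data set, the treatment estimate was 1.13973 (SE 0.55074) both with and without sequence.

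At 30/30 the carry-over shift is -L/2. With L = 0.74 the estimate is 1.48 - 0.37 = 1.11. A period term gives the same 1.11, so it does not repair carry-over either.

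**3. How likely carry-over is.** Sections 7.4.1 and 10.1 require at least 14 days of washout: 14 x 24 / 4 = 84 half-lives.

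**4. Omitted period effect, end-of-period values, 30/30.** The estimate is unbiased, but the variance used in the test is about 16 + p^2 instead of 16. The standard error is therefore too large by sqrt(1 + p^2/16) = 1.008, 1.031 and 1.118. Simulated results:

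| Shift p | Power without period | Power with period | Type I error without period |
|---|---|---|---|
| 0.5 | 80.1% | about 80.5% | 4.8% |
| 1 | 78.8% | about 80.5% | 4.3% |
| 2 | 73.4% | about 80.5% | 2.8% |

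**5. Unequal completers.** The bias is -p x (n_S - n_P)/N. At 34 sildenafil-first and 26 placebo-first it is -p x 8/60: -0.13 at p = 1 and -0.27 at p = 2. Power without the term is then about 70% and 55%, against about 80% with it. The opposite split biases upwards by the same amount.
- Hypergeometric chance of 26/34 or worse, in either direction: 6.9%. Mean absolute imbalance: 5.1% of N, so the mean absolute bias is 0.03, 0.05 and 0.10 point for p = 0.5, 1 and 2.
- Type I error without the term is about 5.0% at 26/34. From 25/35 it rises above 5%: 5.4% at p = 1 and 6.4% at p = 2. The chance of that split or worse is 1.9%.
- Averaged over all splits, type I error is 4.9%, 4.5% and 3.4% for p = 0.5, 1 and 2.

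**6. Within-period change instead.** The contrast is (Visit 3 - Visit 2) - (Visit 5 - Visit 4). A pure level shift that is present at Visits 4 and 5 cancels, so its bias and power loss are zero.

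**7. Cost of adding period.** At effect size 0.37, exact power is 80.5% with 58 df at 30/30, and 79.8% with the term at 26/34.

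**The case against.** The strongest reply is that little depends on this.

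- Section 7.1 puts pharmacology and washout first and treatment order only second. Sections 2.1.2 and 3.1 also cite clinical worsening in pulmonary arterial hypertension after a 2-week washout, as a sign that the effect is gone by then. Section 15.1 plans to summarise outcomes across the washout and against baseline, although to inform later trials. This stands: it makes carry-over unlikely. It does not make the quoted sentence correct.
- The missing period term is inferred from silence. Section 15.1 lists adjustment variables and does not name a random subject effect either, and 15.4 shows that the authors had period in mind. This also stands in part. The figures above describe the models if fitted as listed; the documents do not say that period was deliberately left out.
- Nothing in the documents points to a common shift. RA drugs are to be stable, and visits are to be at consistent times of day (15.3.1). Covariates re-measured at each visit could absorb part of any shift. Under a within-period-change reading a level shift cancels.

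A reader might infer that 7.1 and 15.4 flatly contradict each other. The documents do not support that: 15.4 is about testing an interaction and 7.1 about adjustment. They sit awkwardly together, because 15.4 recognises an aliasing that should have warned against the claim in 7.1.

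**Conclusion.** The point holds at low severity. The sentence in 7.1 is statistically wrong, since a sequence term does not remove carry-over from the treatment contrast. Both model descriptions omit a standard cross-over term.

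A reader might go further and conclude that the trial's estimate is biased by carry-over. The half-life and washout argue against that, and the documents show no residual effect. A reader might also infer that the missing period term inflates false positives or threatens the primary conclusion. On average it does the reverse. The test is conservative, bias averages zero, and the power loss at 30/30 is under 2 percentage points unless the shift approaches 2 points. Type I error above 5% needs a split of 25/35 or worse, a 1.9% chance.

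These sizes rest on an assumed shift, an SD of 4 for the paired difference, dropout unrelated to sequence and an end-of-period contrast. Whether the plan should use end-of-period values or within-period change is a separate question and is not decided here.

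**What to change.** 1. In 7.1, replace the quoted sentence with a statement that the plan relies on the washout and short half-life to avoid carry-over, and that the sequence term does not correct for it. This also brings 7.1 into line with 15.4.
2. In the synopsis and 15.1, list for both the Aim 1 and Aim 2 models: treatment, a fixed period effect (first versus second treatment period), sequence, a random subject effect, and the covariates already planned.

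The cost is wording in three places and one degree of freedom. Sample size, visits and data collection do not change.

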7.2 Phase one

7.2.1 Screening phase (up to 4 weeks)

After signing the informed consent document, subjects will undergo a screening to include baseline labs (creatinine and LFTs and HIV and urine pregnancy test) and review of the inclusion/exclusion criteria. This will include the Consent & HIPAA process.

Note: Screening and baseline can occur on the same day if clinical labs (creatinine and LFTs) have been drawn as part of routine care within 90 days of the baseline.

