7.3 Phase two

7.3.1 Initial Study Treatment phase (Month 0 to Month 3)

Once Screening is fully satisfied, participants will proceed to the Baseline visit. At the Baseline study staff will dispense Study Drug.

Note: Screening and baseline can occur on the same day if clinical labs (creatinine and LFTs) have been drawn as part of routine care within 3 months of the baseline.

Participants will begin use of study drug the day after baseline visit and will remain on that regimen (changes notwithstanding) for 3 months (+/- 7 days).

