8.2 Exclusion criteria

Subjects who meet any of the following criteria will be excluded from enrollment in the study:

- 1) Aged <18 years old
- 2) Pregnant women
- 3) Known personal history of CVD: clinical diagnoses of
 - a. stroke,
 - b. transient ischemic attack,
 - c. myocardial infarction,
 - d. acute coronary syndrome,
 - e. peripheral arterial disease,
 - f. percutaneous coronary intervention
 - g. coronary bypass graft surgery
- 4) Use of high-dose statins (i.e., atorvastatin 40-80 mg/day or rosuvastatin 20-40 mg/day) currently or within past 3 months, or any dose changes of statins or of blood pressure medications that may affect endothelial function (i.e., angiotensin-converting-enzyme [ACE] inhibitors or angiotensin receptor blockers [ARBs]) within past 3 months. If on statin or an ACE-inhibitor or ARB, there should be no anticipated dose changes over the next 6 months.
- 5) Persons with intra-cardiac and intra-pulmonary shunts, unstable cardiopulmonary conditions, or anyone on chronic oxygen therapy
- 6) Persons taking nitric oxide donors, organic nitrites and nitrates, such as glyceryl trinitrate (nitroglycerin), sodium nitroprusside, amyl nitrite ("poppers")

- 7) Severe hepatic impairment (liver function tests >1.5 times upper limit of normal) within past 4 weeks
- 8) Severe impairment in renal function (serum creatinine \geq 1.5 mg/dL) within past 4 weeks
- 9) Hypotension (defined as blood pressure [BP] <90/60)
- 10) Hereditary degenerative retinal disorders (including genetic disorders of retinal phosphodiesterases)
- 11) Persons already taking (or taken within 3 months) sildenafil or other PDE inhibitors (i.e., tadalafil, vardenafil)
- 12) Persons unable to provide voluntary written informed consent
- 13) Severe hypertension (BP >170/110)
- 14) Persons with HIV/AIDS

8.3 **Justification of selection criteria**

The selection criteria were carefully selected to exclude subjects from the study who may potentially be exposed to specific risks after administering the study drug as well as subjects with conditions that may have an impact on the aims of this study.

Subjects over 65 years old will be excluded due to safety concerns regarding use of the 50 mg daily dose of sildenafil in this age group, and inability to achieve blinding with 25 mg daily dose due to altered pharmacokinetics of the drug if over-encapsulated.

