10. STUDY PROCEDURES

10.1 Timing of procedures

Screening and baseline visits can occur on the same day.

- Visit Windows

There are windows of time specific to any given visit in which the visit may take place without deviating from the protocol by being “Late” or “Early”.

- Baseline Visit must occur within 28 days of Screening, otherwise, Screening must be repeated.
- Three Month Visit must occur three months +/- 7 days after Baseline
- The Two Week Washout Visit must take place between fourteen and seventeen days after Three Month Visit
- Six Month Visit must occur three months +/- 7 days after the Two Week Washout Visit

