10.2 Visit Breakdown

10.2.1 Visit 1 – Screening

Screening evaluations will occur after the subject has provided written informed consent. The following evaluations will be performed and information obtained up to 28 days before baseline randomization and the start of study drug treatment:

- Patient information and obtaining of written informed consent
- Eligibility: Assessment of inclusion and exclusion criteria
- Demographic data, including age, gender and ethnicity
- Complete medical history (obtained through patient interview and medical record review)
- Liver function tests and creatinine with GFR. Labs obtained as part of routine clinical care up to 3 months prior to screening will be accepted.
- HIV 1/2 test (results within 3 months prior to screening will be accepted)

If re-screening is required, the liver function tests, creatinine, HIV 1/2 test results, and urine pregnancy test (if applicable) from the previous screening visit may be used if no longer than 3 months prior.

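### Entry rules accept liver and kidney results about three months old, while exclusions #7 and #8 look back only four weeks

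*Combined protocol and SAP*

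**What the plan says.** Section 8.2 of the combined protocol and SAP sets two laboratory exclusions with a four-week look-back. Exclusion #7 reads "Severe hepatic impairment (liver function tests >1.5 times upper limit of normal) within past 4 weeks". Exclusion #8 covers severe renal impairment, with a serum creatinine threshold and the same look-back: "1.5 mg/dL) within past 4 weeks".

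The operational sections use longer windows for the same tests:

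- Section 7.2.1 permits same-day screening and baseline "if clinical labs (creatinine and LFTs) have been drawn as part of routine care within 90 days of the baseline".
- Section 7.3.1 gives the same permission in months: the labs must "have been drawn as part of routine care within 3 months of the baseline".
- Section 10.2.1, on liver function tests and creatinine at Visit 1, states: "Labs obtained as part of routine clinical care up to 3 months prior to screening will be accepted".
- Section 10.2.1 also covers re-screening. Liver function and creatinine results "from the previous screening visit may be used if no longer than 3 months prior".
- Section 10.1 sets the gap between the visits: "Baseline Visit must occur within 28 days of Screening, otherwise, Screening must be repeated".

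**The concern.** A threshold defined over the past 4 weeks can be checked only with a result from those 4 weeks. The entry rules let a much older routine-care result stand in for it, and no later step obtains a newer one. The blood samples listed for Visits 2 to 5 (sections 10.2.2 to 10.2.5) cover biomarkers, nitrite, lipids, homocysteine, lipoprotein(a), glucose and insulin. None includes creatinine or liver function tests. The accepted result is therefore the only mandated laboratory check of these two exclusions.

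What is at stake is subject safety and a clear eligibility rule. Section 8.3 explains that the criteria are there partly to keep out subjects whom the study drug could put at risk. Every subject is assigned 50 mg daily in one of the two periods, and the plan has no lower dose, so entry screening carries much of the protection. There is also a compliance problem: a 60-day-old result satisfies section 7.2.1, yet a monitor could record it as an eligibility deviation under section 8.2.

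**Working it through.** The plan gives no figure to reproduce here. The check compares the greatest accepted age of a result with the look-back in the criterion.

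**Inputs**

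- Look-back in exclusions #7 and #8 (section 8.2): 4 weeks = 28 days.
- Same-day allowance: 90 days before baseline (7.2.1), or 3 months (7.3.1).
- Routine-care allowance at Visit 1 (10.2.1): 3 months before screening.
- Longest screening-to-baseline gap (10.1): 28 days.
- Three calendar months last 89 to 92 days, depending on the dates.

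**Same-day screening and baseline (7.2.1)**

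- Days outside the window: 90 − 28 = 62.
- Ratio to the window: 90 / 28 = 3.2.

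**Separate visits, both limits reached**

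- Age at baseline = age at screening + gap: 89 + 28 = 117 to 92 + 28 = 120 days.
- Days outside the window: 117 − 28 = 89 to 120 − 28 = 92.
- Ratio to the window: 117 / 28 = 4.2 to 120 / 28 = 4.3.

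**Four weeks counted from screening instead of baseline**

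- Days outside the window: 89 − 28 = 61 to 92 − 28 = 64. The mismatch does not depend on the anchor.

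**Labs drawn at the screening visit**

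- Age at baseline is at most 28 days, inside the window. These subjects are not affected.

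**Does another step supply a newer value?**

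| Step | Requires a new creatinine or liver result? |
|---|---|
| Medical record review at Visit 1 (10.2.1) | No |
| Eligibility reconfirmation at baseline (10.2.2), listed for separate visits only | No |
| Eligibility reconfirmation at Visits 3 to 5 (10.2.3 to 10.2.5) | No |
| Blood samples at Visits 2 to 5 | Neither test is listed |
| Withdrawal if an exclusion other than #4 develops (8.4) | No |
| Re-screening (10.2.1) | No; earlier results may be carried forward |

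**The case against.** The strongest reply is that the two sets of text do different jobs. Exclusions #7 and #8 exclude subjects who have had hepatic or renal impairment in the past 4 weeks; neither says that a test from those weeks must exist. Section 10.2.1 sets the rule of evidence and accepts 3-month results. On that reading, a subject with an acceptable 3-month result and no known impairment since then is eligible under both. The longer window also appears in three sections and again for re-screening, which looks like a deliberate choice to allow same-day visits. If so, the remedy may be no more than rewording #7 and #8.

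That reading is possible, but it lets missing data satisfy a safety exclusion. Someone whose only result is 29 to 90 days old passes because nothing was measured. If 3-month evidence was intended, the criteria should state it.

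Some of the reply stands:

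- A newer abnormal routine-care result, if found, would lead to exclusion or to withdrawal under section 8.4. This reduces the risk without closing the gap.
- The ratios above compare calendar windows and do not measure risk. The documents give no rate of newly abnormal results and do not show that 3-month labs are unsafe in this population.
- The 117 to 120 days require two limits to be reached together, so 90 against 28 days is the main figure.
- Endpoints, sample size, alpha and the randomized comparison are untouched.

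**Conclusion.** The concern holds. As written, the protocol lets a subject be randomized and given study drug with no creatinine or liver result inside the window that its own exclusions name. The qualifying result can be 62 days outside that window on the same-day path, and 89 to 92 days outside when separate visits reach both limits. This takes 4 weeks as 28 days and three calendar months as 89 to 92 days; changing the anchor from baseline to screening does not remove the mismatch. It affects only subjects who enter on routine-care or carried-forward results, and their number cannot be determined from the documents. It is an eligibility and safety inconsistency that should be corrected, with no effect on the statistical inference.

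**What to change.** In sections 7.2.1, 7.3.1 and 10.2.1, accept creatinine and liver function results only if drawn within 28 days before baseline, matching exclusions #7 and #8. Apply the same limit to results carried forward at re-screening. Where no such result exists, repeat the tests and review them before study drug is dispensed. The cost is protocol wording, some repeat blood draws and fewer same-day screening and baseline visits.

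If the sponsor judges 3-month results adequate, amend exclusions #7 and #8 to a single 3-month window counted from baseline, and use that same window and anchor in the other three sections. This needs no extra draws when visits fall on one day, but it loosens the stated criteria, so the protocol should give the reason.
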